As of July 2021, **32 Carilion psychiatric clinicians** are engaged in Owl Insights, an MBC vendor. Approximately **500 unique individuals complete monthly PROMs** through this system as part of routine clinical care. Our research group recently conducted analyses of nearly 900 ambulatory adult psychiatric patients in ambulatory psychiatry at Carilion Clinic (CC&PBM) engaging in PROMs via telepsychiatry and in-person modalities. PROM results of a patient cohort in clinical care prior to the onset of COVID-19 (November 2019) through March 2021 demonstrated that depression, anxiety and psychological functioning did not decline as hypothesized but statistically improved (Kablunger, et al., 2021). Data also show that the **engagement rates range from 33 to 74% depending on demographic factors**, and completion rates were significantly different for diagnostic group and payor status of the patient (Kablunger, et. al, 2021). The standard goal for MBC utilization is 80%, while the department goal is to have **all** patients participate in PROM completion. Our research group has also completed focus groups of psychiatric clinicians and staff with regards to Owl Insights and PROMs within the past year, identifying barriers and facilitators to its use and plan training implementation for improved adherence and satisfaction (summary of focus group data and training outline- included in grant application, IRB approved protocol 20-1065). Since March 2020, CC-P&BM has been engaging with patients via telephone and several telehealth platforms. Currently, ambulatory psychiatry uses AmWell, a telehealth platform that provides secure telemedicine visits between clinician and patient. The department has documented between **2100-2300 adult telemedicine sessions monthly and 200-700 in-person visits per month** between June 2020 and June 2021.

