CC-P&BM currently has a wait-list of over 300 adults referred for mental health evaluation and treatment. Access to psychiatric clinicians remains insufficient despite increasing numbers of providers in our clinic and the mental health needs associated with the pandemic are rising. As a result, a clinical intake coordinator (Licensed Professional Counselor) began in the CC-P&BM ambulatory clinic September 2021. This coordinator will individually contact people on the wait-list for psychiatric care by phone as part of routine care, beginning with the referrals most remote in time. The coordinator will complete an intake assessment for each wait-list individual who wants a psychiatric referral. Prior to the initial intake assessment by the intake coordinator, wait-list individuals will receive a bundle of PROMs automatically (through Owl Insights) to complete. These measures include the PHQ-9, GAD-7, BASE-6, DAST-10, USAUDIT, Covid Event Checklist and the Adult Behavioral Health Screen (ABHS), all of which are currently used in routine ambulatory care. The intake coordinator will complete the intake assessment, noting the completion, and scores of, the PROMs. Scores of the PHQ-9, GAD-7 and BASE-6 will be utilized to triage the most severe referrals and move them up for a sooner appointment (the triage system of scores and Nurse-Practitioner vs Medical Doctor screening questions are attached to this application). Any concern about patient safety is also addressed immediately during this intake and is also noted in the materials attached to this application. **Up to this point, all intake coordinator/referral interaction are part of routine care.**

If eligible and capable of consent based on intake coordinator clinical judgement, individuals will then be randomized to participate to the no intervention group (completion of screening PROMs only during the intake coordinator assessment) or the minimal intervention group (intake coordinator assessment, including PROM screening and then prospective monthly PROM completion in addition to assigned microlearning

patient education videos). We will analyze changes in PROM scores for individuals engaged in both wait-list groups and compare results to their PROM scores at the initial provider telemedicine visit and over time (6 months post first provider assessment). Consent may be in-person with hard copy consent forms and signatures or through e-Consent either in-person using ipads or remotely using REDCap.

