10.6 State the research hypothesis or the question that the research will answer.

List the research objectives and expected outcomes. A primary outcome or objective must be identified. After the statement of the primary objective, secondary objectives may be listed. Objectives should be simple and specific.

Aim 1 will use PROMs to assess the symptomology and well-being of adult individuals on a wait-list group referred to CC-P&BM clinic from their initial referral to their initial psychiatric session.

In particular, we propose randomizing wait-list individuals to one of two groups to assess the influence of time alone awaiting initial psychiatric clinician assessment (no intervention) versus minimal intervention using prospective monthly repeated PROMs and viewing microlearning patient education videos while awaiting initial psychiatric clinician assessment.

Aim 2 will use PROMs to determine whether there is a difference in clinical symptomology and well-being for patients during telemedicine treatment with their practitioner compared to wait-list individuals.

10.7 State how qualitative and/or quantitative data will be analyzed in order to answer the research questions.

Include an analysis from a statistician (or someone familiar with statistical methods) that either indicates the power calculation for the sample size necessary to meet the primary study outcome or objective OR a statement from the statistician indicating reasons why a power calculation is waived or not necessary for this study. Also include the statistical test(s) that will be used to analyze your primary study objective (t-test, chi-square, etc.). Secondary outcomes may be listed as descriptive.

If this is a proof of concept or feasibility study that includes limited efficacy testing, please provide a description on how your design will determine if an intervention should be recommended for broader efficacy testing. If a study is meant to be solely descriptive, then the primary outcome or objective must be limited in scope. As such, the study results apply only to the sample being studied, and conclusions cannot be drawn about the larger population.

This is required for ALL studies, as this section helps the IRB confirm the data being collected are relevant to the study aims and planned analysis.

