The primary outcome of interest is the change in total PROM score for each assessment required of patients enrolled in the study. Initial PROM scores will be acquired and assessed after referral into the CC-P&BM program. The potential to receive few records per patient is believed to be relatively high; therefore, the final PROMs completed for each assessment will be used to determine the change in total score. This change will be compared between patients receiving telemedicine and those of the control (wait-list) groups. A two-sample t-test or non-parametric equivalent of the mean change in total PROM will be performed to determine if the change is significantly different among treatment types. An alpha of 0.05 will be used to assess statistical significance. Univariate and multivariate analyses may occur to measure numeric variables by measures of central tendency and variation and categorical variables by frequencies and percentages. Trends of PROM scores will be evaluated between treatment types by the time in program.

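### Section 10.7's two-sample test for Aim 2 ignores shared clinicians and possible reuse of the same patients, so its standard error is not valid as planned; the documents do not fix the direction of the error.

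*Combined protocol and SAP*

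**What the plan says.** Section 10.6, Aim 2, asks about symptoms and well-being "for patients during telemedicine treatment with their practitioner compared to wait-list individuals". Section 10.7 defines the outcome as change in total PROM score and states "This change will be compared between patients receiving telemedicine and those of the control (wait-list) groups". Its one inferential method is "A two-sample t-test or non-parametric equivalent of the mean change in total PROM will be performed", and "An alpha of 0.05 will be used to assess statistical significance". The univariate and multivariate analyses that may follow are described only as summaries, and the trends over time are given no model. No section mentions a clinician term, a patient term or a clustered standard error.

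On clinicians, section 10.5 reports "32 Carilion psychiatric clinicians" engaged in the PROM system as of July 2021. It does not say how many will treat study patients or with what caseloads.

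On who is in each condition, the documents point two ways. Sections 10.4 and 10.5 describe treated patients set against untreated referrals over the same period, which reads as separate people. Section 10.5 also says that the wait-list groups will be analysed to "compare results to their PROM scores at the initial provider telemedicine visit and over time (6 months post first provider assessment"), and section 19.1 follows both randomised groups for six further months after the first provider evaluation. That reads as the same people in both conditions. Enrolment is 200 (11.2), with 100 in the no-intervention group (11.3). No telemedicine group size is given. On the baseline, section 10.7 says only "Initial PROM scores will be acquired and assessed after referral into the CC-P&BM program".

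**The concern.** A two-sample t-test, or its rank equivalent, takes its standard error from the assumption that all observations are independent. Two features of Aim 2 break that assumption.

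- **Shared clinicians.** A treated patient's change includes whatever is common to that clinician's patients. Wait-list periods have no treating clinician, so the clustering lies in one condition only.
- **Shared patients.** If a participant supplies a wait-list change and then a treatment change, the two are correlated, and an unpaired test ignores this.

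At stake is whether the Aim 2 p-value means what the stated 0.05 level says. Dealing with one feature does not deal with the other: pairing within patients leaves the clinician component in place, because it enters only the treatment-phase change. Nor can the problem be checked later if the data lack a clinician code. The REDCap fields that section 9.15 lists as visible to the external data manager contain none. (The attached data collection sheet is not among the documents available here.)

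**Working it through.** **The plan's own figure.** The enrolment of 200 cannot be reproduced, because no effect size, SD, power, dropout or ICC is given. The check below therefore concerns only the type I error of the planned test.

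**Inputs from the documents.** Level 0.05 (10.7; taken as two-sided, since sidedness is not stated); 32 clinicians (10.5); 200 participants (11.2); 100 in one wait-list group (11.3).

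**Assumptions.** Clinician ICC of 0.02, 0.05 or 0.10; equal caseloads; equal variances and equal numbers in the two conditions; 10 clinicians as an alternative to 32. The documents give none of these.

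**Step 1: clinician clustering alone.** With n patients per condition and k clinicians:

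- design effect DEFF = 1 + (n/k − 1) × ICC, in the treated condition only
- variance ratio (true over assumed) R = (DEFF + 1)/2
- actual type I error = 2 × [1 − Φ(1.96/√R)]

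Example, n = 200, k = 32, ICC 0.05: n/k = 6.25, DEFF = 1 + 5.25 × 0.05 = 1.2625, R = 1.131, type I error 0.065. With ICC = 0 the formula returns 0.050.

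| n per condition, clinicians | ICC 0.02 | ICC 0.05 | ICC 0.10 |
|---|---|---|---|
| 100, k = 32 | 0.052 | 0.056 | 0.062 |
| 200, k = 32 | 0.056 | 0.065 | 0.081 |
| 200, k = 10 | 0.072 | 0.107 | 0.160 |

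In the last cell DEFF = 1 + 19 × 0.10 = 2.90, R = 1.95 and √R = 1.40, so the true standard error is 40% larger than the naive one. Simulated t-tests at ICC 0.05 gave 0.059, 0.066 and 0.104 for the three rows.

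**Step 2: the same 200 patients in both conditions.** Enrolment is 200, so 200 versus 200 drawn from the enrolled participants would be the same people twice. Let ρ be the correlation between a patient's wait-list change and treatment change. Then R = (DEFF + 1 − 2ρ)/2.

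If scores at the three time points have equal variances and equal correlations, ρ follows from the baseline:

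- both changes measured from referral: ρ = +0.5
- treatment change restarted at the first provider visit: ρ = −0.5

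| Baseline, clinicians | ICC 0 | ICC 0.02 | ICC 0.05 | ICC 0.10 |
|---|---|---|---|---|
| Common (ρ = +0.5), k = 32 | 0.006 | 0.008 | 0.014 | 0.025 |
| Common (ρ = +0.5), k = 10 | 0.006 | 0.018 | 0.047 | 0.104 |
| Successive (ρ = −0.5), k = 32 | 0.110 | 0.116 | 0.125 | 0.140 |
| Successive (ρ = −0.5), k = 10 | 0.110 | 0.132 | 0.163 | 0.211 |

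Simulation at k = 32 and ICC 0.05 gave 0.016 (common) and 0.123 (successive). With a common baseline the level is exceeded only when DEFF is above 2, that is, ICC above 1/5.25 = 0.19 with 32 clinicians or 1/19 = 0.053 with 10.

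**Step 3: correct the pairing but not the clinicians.** A paired test assumes variance proportional to 2 − 2ρ, so R = (DEFF + 1 − 2ρ)/(2 − 2ρ). At ICC 0.05:

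- ρ = +0.5: R = 1.2625 with 32 clinicians (type I error 0.081) and 1.95 with 10 (0.160)
- ρ = −0.5: R = 3.2625/3 = 1.0875 (0.060) and 3.95/3 = 1.317 (0.088)

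**The case against.** The strongest case against has four parts.

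- **Unknown inputs.** No ICC, caseload or number of treating clinicians is documented, and the 10-clinician rows have no source. At the one documented count the clinician effect is small. Section 10.5 reports past PROM engagement of 33 to 74%; applied to 200 this leaves 66 to 148 patients, and at ICC 0.05 with 32 clinicians the type I error is only 0.053 to 0.061. This stands: the figures are illustrations over a range.
- **Direction.** A reader might infer that the Aim 2 standard error is too small and that the 0.05 level is breached. The documents do not support that as a fact. It follows if the two conditions are different people and the ICC is positive. If the same patients serve in both with a common referral baseline, the test is usually conservative. This also stands, but the conservatism comes from two errors that partly offset, and step 3 shows that repairing only the pairing brings the clinician error out.
- **Target of inference.** If conclusions were confined to these clinicians, differences between them would not be sampling error. That is a fair reading for a single clinic. Yet sections 10.4 and 10.5 frame the question as the impact of telemedicine, and section 23.12 expects results to inform other systems, although for wait-list groups. The plan should say which it means.
- **Case mix.** Section 10.5 refers to screening questions that separate nurse-practitioner from physician referrals, so differences between clinicians may partly reflect their patients. A clinician random effect does not remove that. This is a limit of the remedy, not a defence of the planned test.

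Section 10.7 plans a test and no interval, so the point concerns the standard error and p-value.

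**Conclusion.** The omission is real: the only inferential method for Aim 2 assumes independence that the design does not provide, so its standard error is not valid as planned. The size is conditional. Clinician clustering alone is a modest problem at 32 clinicians and a material one only if far fewer treat study patients. Overlap of patients between conditions may matter more: at 32 clinicians and ICC 0.05 the type I error would be about 0.014 or about 0.125, depending on a baseline that section 10.7 does not settle. All of this rests on the assumed ICCs, equal caseloads and the equal-correlation values of ρ. The figures are for the t-test; a rank test makes the same independence assumption but was not computed. The randomised comparison of no intervention with minimal intervention during the wait involves no treating clinician and is not affected.

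**What to change.** 1. Add a coded treating-clinician ID to REDCap and to the de-identified export. Section 23.1 routes suicidality alerts to the primary provider once treatment has begun, so the link from patient to clinician should already exist.
2. In section 10.7, state for Aim 2 whether the same patients supply both conditions, and which baseline each change uses.
3. Replace the two-sample test for Aim 2 with one of the following:
   - a mixed model with a patient random effect and a clinician random effect in the treatment phase only, with Satterthwaite or Kenward-Roger degrees of freedom. Fit it to the scores, or leave the covariance of the two changes free, because a patient intercept on change scores cannot represent a negative ρ;
   - clinician-clustered standard errors with a small-sample correction. If each patient has one clinician and the wait-period record is placed in that clinician's cluster, this also covers the within-patient dependence.

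The cost is one coded field, a few sentences in section 10.7 and a possibly wider Aim 2 interval. Aim 1 needs no change on this account.

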10.8 Statistical Review

Name of statistician or person who prepared the statistical plan:	Department/Institution:	Date statistical review was conducted:
---	-------------------------	--

***Note: The statistician or individual that prepared the statistical plan must also be included on the study team if they meet the definition of key research personnel (ex: significantly involved in the study design, conduct, or reporting of the research).**

If a statistical review has not been submitted, explain why:

NA

10.9 Do you want to view the minimal risk exempt categories to determine if your research may qualify for exemption before completing the full application? Please note that determination of exemptions must be made by the IRB.

Your research may be Exempt from future IRB oversight if it only involves retrospective review of data (including Limited Data Sets), non-sensitive interviews or surveys, or falls into other minimal risk categories. If the research is determined to be exempt by the IRB, you will not be required to complete a full IRB application. If you complete the Exempt application and the IRB determines your research is not exempt, you will be required to complete the full IRB application.

Yes No

11.0

Subject Population

11.1 Please select the population(s) being targeted, or likely to be included in this research study. (select all that apply)

- Medical Chart Review of patients only (no in-person contact)
- Normal Adults/Healthy Volunteers
- In-Patient Population
- Out-Patient Population
- Patients in emergency situations
- Terminally ill patients
- Employees/Staff
- Students
- Children/Minors (anyone younger than 18 years of age in the state of Virginia. For research conducted outside of the state of Virginia, age of majority is dependent on state/local law)
- Prisoners
- Pregnant Women
- Fetuses
- Neonates of uncertain viability and/or nonviable neonates
- Adults with Impaired Decision-Making Capacity
- Persons with Limited-English proficiency (LEP) or Non-English Speakers
- Individuals of Childbearing Potential

11.2 Please indicate the total number of subjects anticipated to be enrolled at this site/by this investigator.

For the purposes of the IRB, a subject is enrolled once they have provided consent to participate, or for studies approved with a waiver of consent, once data has been collected on the subject.

200

11.3 If the research involves multiple subject groups or cohorts at this site, provide the anticipated number of subjects in each of group or cohort (e.g., control/experimental, adults/children, etc.).

wait-list (no intervention)- 100

11.4 Provide the age range for the proposed subject population (e.g., 0-5 years old):

18-99

11.5 Specify the inclusion criteria for each of the subject groups to be included in the research.

If there are multiple different groups being recruited with different eligibility criteria, instead add an Eligibility Criteria checklist for each group as a supplemental document after you complete this application. Please make note of this in the Inclusion Criteria below.

Order Number	Criteria
1	Although there are two wait-list conditions (no intervention vs minimal intervention), all potential subjects must be 18 years old or above and provide consent for randomization. Potential subjects must have the ability to complete PROMs either by cell phone or through email.
2	New adult ambulatory psychiatry patients seen in the psychiatry clinic between 11.1.21 and 4.5.22 assessed by the intake coordinator [name].

11.6 Specify the exclusion criteria for each of the subject groups to be included in the research.

If there are multiple different groups being recruited with different eligibility criteria, instead add an Eligibility Criteria checklist for each group as a supplemental document after you complete this application. Please make note of this in the Exclusion Criteria below.

Order Number	Criteria
1	Patients who do not (or are unable to) provide consent for participation or do not have the ability to complete PROMs or watch microlearning videos remotely.
2	Intellectual disability or non-verbal
3	Patients with neurocognitive disorders who do not have the capacity to undergo informed consent and participate in the study

11.7 Is information being obtained about individuals other than the “target subjects” (such as a family member or colleague of the subject), making the other individuals “secondary subjects”?

Yes No

12.0 Pregnant Individuals, Individuals of Childbearing Potential, Breastfeeding Infants, Fetuses, or Neonates**12.2 Are there any additional risks to pregnant individuals by participating in this study?**

If your research involves fetuses or neonates, please contact the IRB prior to submission.

Yes No

12.3 Are there any additional risks to individuals of childbearing potential, individuals who become pregnant, breastfeeding infant, or fetus or neonate by participating in this study?

Yes No

13.0

Informed Consent for Adult Subjects

13.1 How do you plan to obtain consent from ADULT subjects or their Legally Authorized Representative?

Check all that apply:

- Written consent document with signature (ie: obtaining signature from subject or Legally Authorized Representative)
- Waiver of written documentation of consent (ie: consent will be obtained through verbal confirmation from the subject or Legally Authorized Representative rather than through a signed document)
- Waiver of informed consent for minimal risk research (ie: typically appropriate only when the study does not involve any interaction or intervention with subjects)
- Waiver or alteration of the elements of informed consent (ie: research involving deception)
- Waiver of the informed consent document and process for PLANNED EMERGENCY RESEARCH. Contact the IRB before submission.
- No adults are being enrolled; this study is only enrolling children. (You will answer questions about the assent and parental permission process later.)

You must attach all consent forms, consent scripts, and information sheets in the Initial Submission Packet.

13.2 Is it expected that surrogate consent will need to be obtained from Legally Authorized Representatives (LARs) for some or all adult subjects?

Yes No

13.3 If the research includes more than one subject group or you have selected multiple responses above due to the inclusion of multiple subject groups, please specify the requested consent method for each group, or state N/A.

The requested data from normal standard of care PROM completions (11.1.21-4.5.22) does not include consent as it is part of our clinical care with all ambulatory patients.

The signed informed consent was obtained for all participants in the study from 4.6.22 to present today.

